#### 4 STUDY DESIGN AND METHODS

#### 4.1 Study Overview

This will be a single-site, randomized-within-subject, placebo-controlled, double-blind phase 2 pilot study in which all subjects receive both active drug (dexamethasone) and placebo (normal saline), thereby acting as their own controls. Subjects are required to enter this study from SS protocol 84-D-0056. Subjects will have one parotid gland treated with dexamethasone irrigation and the other gland treated with normal saline irrigation. The study design is doubly-repeated measures; within a subject, measures are repeated in both time and treatment (i.e., one side of mouth receives placebo while the other receives dexamethasone).

Subjects will be required to attend a minimum of 7 out-patient clinic visits for study assessments and procedures. The maximum duration of on-treatment study participation for each subject is

expected to be up to approximately 11 weeks, with an approximate Screening interval of up to 3 months and an additional Safety Follow-up period of approximately 15 days.

#### 4.2 Recruitment

Subjects will be recruited from the subjects enrolled in Sjögren's Clinic Protocols and other sources, including physician referrals, self-referrals, Patient Recruitment Public Liaison, and www.clinicaltrials.gov. Recruitment will include flyers for patients and physicians as well as dear doctor letters. Flyers will be distributed to the Sjögren's syndrome network at John's Hopkins, the Sjögren's Syndrome Foundation, attendees at the annual American College of Rheumatology (ACR) meeting and to other local physicians and dentists. Recruitment efforts will also include posts on the NIH Facebook and Twitter accounts. Patients not already enrolled in 84-D-0056 will be required to enroll to confirm the diagnosis of primary Sjögren's syndrome. Estimated recruitment time will be up to two years.

#### 4.3 Screening

Subjects who have been diagnosed with primary SS in Protocol 84-D-0056 will be eligible for participation. Subject consent will be obtained before any study activities or procedures. Screening will be conducted up to 12 weeks before Day 0 in two stages (Stage I & Stage II) to minimize procedures for subjects who do not meet initial salivary flow criteria. Multiple visits will be needed to complete the screening portion of the protocol.

Stage I screening assessments will be done within 6 weeks prior to Stage II and will include vital signs, medical and medication history, review of concomitant medications and evaluation of salivary flow. If salivary flow meets eligibility criteria the following additional Stage I procedures will be done: physical examination, pregnancy testing, routine clinical laboratory tests, and review of previous MSG biopsy. If the subject continues to meet eligibility for study participation according to the preceding assessments, she will undergo parotid saline irrigation and fill volume measurement. If an MSG biopsy has not been performed within 7 years of screening and an MSG biopsy needs to be performed, the saline irrigation and fill volume measurement will occur after the results of the MSG biopsy are obtained, as the final assessment of Screening Stage I.

Screening Stage II will be done within 6 weeks prior to Day 0 and will include vital signs, administration of the dry mouth questionnaire (Appendix 24.7), Sjogren's Disease Activity Index (Appendix 24.9), laboratory blood assessment for baseline values, magnetic resonance imaging, and technetium scan, and a parotid core needle biopsy. For the Screening Stage II, the pregnancy test must be within 24 hours before the technetium and MRI scans (for subjects of childbearing potential). A CBC with differential and platelets, PT, and PTT will be done within 7 days before each of the ultrasound-guided core needle parotid biopsies. All study visit procedures are detailed below in section 4.4 as well as a description of the approximate time to complete each procedure.

[figure not shown]
We will accept results of imaging procedures done elsewhere if completed within 3 months of enrollment (screen-stage 1 visit).

Subjects who randomize and receive one study treatment (Day 0) and take an excluded concomitant medication (immunosupressants) may re-screen. They will not have screening MRI, Technetium scan, or parotid biopsy procedures repeated.

#### 4.4 **Study Procedures**

The study scheme depicted in Figure 4-1 presents the study schedule of events. All procedures described are for the purposes of participation in this study and considered research..

#### Figure 4-1 Study Scheme

a Conducted as last assessment of Stage I, only for otherwise eligible subjects

b Subjects progress to Stage II then to Day 0, based on their qualification as determined by the assessments conducted during the prior Screening stage.

c Conducted as final assessment in Stage II, only for otherwise eligible subjects

#### Table 4-1Schedule of Events

				On-treatment Visits				
	Screen	ing						Safety Follow-up b (15 ± 5 days after Day 56 Visit)
Procedure	Stage I (within 6 weeks before Stage II)	Stage II a (within 6 weeks before Day 0)	Day 0 a	Day 14 ± 5 days	Day 28 ± 5 days	Day 42 ± 5 days	Day 56 -3/+14 days	
Consent	Х							
Inclusion/exclusion criteria	Х							
Relevant medical history/current medical conditions	Х							X 
Vital signs 	Х	Х	Х	Х	Х	Х	Х	X 
Physical examination	Х		Х		Х		Х	X 
Urine or serum pregnancy test 	Х	Х	Х		Х		Х	
Patient Dry Mouth Questionnaire		Х	X 	Х	X 	Х	Х	
Sjögren's Disease Activity Index		Х	X 	Х	X 	Х	Х	
Saliva collection (salivary flow measurement)	$X^4$		$X^4$	Х	X 	Х	Х	
Adverse events evaluation	Х	Х	Х	Х	Х	Х	Х	X 
Concomitant medications	Х	Х	Х	Х	Х	Х	Х	X 
Randomization			Х					
Saline irrigation of parotid glands & determination of fill volume	$X^{10}$							
Randomized irrigation treatment  of parotid glands			Х		Х			
Ultrasound-guided core needle biopsy of right parotid gland 		X 					Х	
Routine clinical laboratory tests 	Х	Х	Х		Х		Х	X 
Blood for immunologic tests 			Х		Х		Х	
Blood for dexamethasone concentration 			Х		Х			
Minor salivary gland biopsy 	Х							
Magnetic resonance imaging		Х					Х	
Technetium scan of salivary glands		X					Х	

CNS and NIDCR IRB Protocol Template (rev.9.21.11)

Re	search blood		$X^{13}$	$X^{13}$	Х					
a	Subjects progress to Stage II then to Day 0, based	on their qualification as	s determined by the assess	ments conducted during	g the prior Screening	stage.				
b	Telephone contact or clinic visit.									
1	Pulse rate, respiratory rate, systolic and diastolic blood pressures, and temperature.									
2	For Stage II screening and Day 56, pregnancy test must be performed within 24 hours before technetium and MRI scans for subjects of childbearing potential. For Days 0 and 28, pregnancy test must be performed before irrigation treatment.									
3	On Days 0 and 28, may be done 2 days before vis	sit or prior to saliva colle	ction.							
4	Performed before irrigation treatments at Stage I	screening and on Days 0	and 28.							
5	Dexamethasone in one parotid gland and normal	saline in the other parotic	d gland.							
6	Baseline ultrasound-guided core needle biopsy will be performed at least 14 days before Day 0. Follow-up biopsy will be performed after the technetium and magnetic resonance imaging scans on Day 56.									
7	Complete blood count with differential and platelets, Chem 14, erythrocyte sedimentation rate, C-reactive protein, and amylase. Prothrombin time and partial thromboplastin time will be obtained at Stage II screening and Day 56. The completed blood count with differential and platelets, prothrombin time, and partial thromboplastin time must be done with 7 days before ultrasound-guided core needle biopsy of the parotid. Clinical laboratory tests will be performed at the Safety Follow-up only if clinically indicated.									
8	Antinuclear antibodies, antibodies to extractable	nuclear antigens, rheuma	toid factor, C3 complement	nt, C4 complement, imm	nunoglobulin (Ig)A,	IgM, and IgG.				
9	Two samples will be obtained: one prior to rando treatment.	mized irrigation treatme	nt of the parotid glands (ba	aseline) and the other 7	5 ( $\pm$ 15) minutes afte	r irrigation				
10	Performed as final step of Stage I, when subject h	as otherwise qualified for	or the study.							
11	Performed as final step of Stage II, when subject	has otherwise qualified	for the study.							
12	2 Performed if a minor salivary gland biopsy is needed based on criteria in Section 3.2. Must be conducted and evaluated prior to any other procedures and activities associated with Stage II screening.									
13	3 On Days 0 and 28, obtained prior to irrigation treatment.									
14	Assessed via telephone. Clinic visit scheduled, if	deemed necessary based	l on medical need or per su	ıbject request.						
15	Performed only if clinic visit deemed necessary pe	er telephone interview.								

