#### 3.3 Exclusion Criteria

- 1. History of lymphoma.
- 2. History of mycosis, aspergillosis, or other deep fungal infection of the parotid gland.
- 3. History of salivary gland malignancy (primary or metastatic to the salivary gland).
- 4. History of secondary Sjögren's syndrome.
- 5. Parotid infection that does not resolve at least 4 weeks before the start of Screening.
- 6. Any active viral infection that does not resolve by the start of Screening.
- 7. Pregnancy or lactation.
- 8. Use of biologics within 3 months of the start of Screening.
- 9. Any experimental therapy within 3 months before the start of Screening.
- Use of immunosuppressants such as methotrexate, leflunomide, azathioprine, cyclophosphamide, systemic cyclosporine, or systemic corticosteroids within 3 months prior to the start of the Screening.
- 11. Use of inhaled corticosteroids within 3 months prior to the start of Screening.
- Use of antimalarials and regular use of NSAIDs unless the dose has been stable (or decreased) for at least 2 months.
- Inability to discontinue the use of saliva stimulants such as pilocarpine and cevimeline for 24 hours before each study visit.
- 14. Parotid intraductal irrigation or instillation with steroids within the past year.

- 15. Use of rituximab within 6 months prior to the start of Screening.
- 16. Allergy to steroids or technetium, or any components of the formulations.
- 17. Current use of warfarin or heparin.
- 18. History of bleeding disorder.
- 19. Both severe atrophy and fibrosis of the MSG noted on the pathology report of the MSG biopsy.
- 20. Inability to comply with protocol procedures and the number of required visits.
- 21. Inability to cannulate one or both parotid glands.
- 22. Parotid fill volume <0.5 mL in one or both parotid glands.
- 23. Significant concurrent medical condition or other circumstances that, in the opinion of the principal investigator, could affect the subject's ability to tolerate or complete the study.
- 24. Unable to understand written English for completion of study questionnaires.

The eligibility checklist is included in Appendix 24.3.

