# 4.4.4 **Patient Dry Mouth Questionnaire**

Subjects will be asked to complete a questionnaire about their dry mouth symptoms (see Appendix 24.7) once during Screening Stage II and on Days 0, 14, 28, 42, and 56. Completing the questionnaire can take up to 15 minutes.

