# 4.4.5 Sjögren's Disease Activity Index

The clinician will use the Sjögren's Disease Activity Index to assess disease activity in each subject (see Appendix 24.9) once during Screening Stage IIand on Days 0, 14, 28, 42, and 56.). This index review takes up to 30 minutes for the clinician to complete.

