#### 6.2 **Concomitant Medication Contingencies**

During the period of the study, subjects will not be allowed to use the following medications: human or murine antibodies, rituximab, warfarin, heparin, immunosuppressants (e.g., methotrexate, leflunomide, azathioprine, cyclophosphamide, systemic cyclosporine, systemic corticosteroids, and intra-articular corticosteroids), or any experimental drug. If it is necessary to prescribe one of these medications, the subject may participate in subsequent treatments, without repeating baseline MRI, NM Scan or Parotid Biopsy, after a washout of 3 months for immunosuppressants Additionally, subjects must refrain from the use of salivary stimulants within 24 hours prior to each study visit. If a subject enters the study on a stable dose of antimalarial drug or NSAID, the dose should not be increased during the study. All effort should be made to maintain stable dosing of other concomitant medications, including saliva substitutes.

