#### 7.10 Risk of stopping salivary stimulants

Subjects will be required to suspend the use of salivary stimulants within 24 hours prior to each study visit, and this suspension could cause discomfort from dryness of the mouth.

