#### 9.2 Secondary Outcome Measures

Secondary endpoints include the following:

- Change in focus score on parotid biopsy from Stage II screening to Day 56.
- Changes in salivary flow from Day 0 to study Days 14, 28, 42, and 56.
- Changes in assessments on the Patient Dry Mouth Questionnaire from Day 0 to study Days 14, 28, 42, and 56.
- Changes in assessments on the Sjögren's Disease Activity Index from Day 0 to study Days 14, 28, 42, and 56.
- Changes in other assessments of salivary function from baseline to study Day 56, including technetium scan of the salivary glands.
- Changes in laboratory measures of inflammation.
- Frequency of AEs related to treatment; location of the AE (body site, right or left), will be recorded and evaluated, as applicable.

Exploratory endpoints will be the changes in mechanistic endpoints from baseline to study Days 14, 28, 42, and 56.

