# 18 ALTERNATIVE THERAPIES

Current standard-of-care therapies for xerostomia due to primary SS are salivary stimulants and topical oral moisturizers. Salivary stimulants may not be used in this protocol within 24 hours prior to saliva collection.

Patients with internal organ manifestations of SS may be treated with systemic corticosteroids or immunosuppressive drugs. During the study, subjects will not be allowed to use human or murine antibodies, rituximab, or immunosuppressants.

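### The Day 0 dry mouth questionnaire may be completed outside the 24-hour stimulant hold while Days 14, 42 and 56 fall inside it, so change from Day 0 can include a stimulant-withdrawal effect

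*Protocol*

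**What the plan says.** Table 4-1 schedules the Patient Dry Mouth Questionnaire and the Sjögren's Disease Activity Index at Screening Stage II and on Days 0, 14, 28, 42 and 56. Footnote 3 is attached to both instruments on Days 0 and 28 only: "On Days 0 and 28, may be done 2 days before" the visit or, as the alternative, ahead of saliva collection. Days 14, 42 and 56 carry no such footnote.

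Stimulant users may enrol. Section 3.3 excludes only those with "Inability to discontinue the use of saliva stimulants such as pilocarpine and cevimeline for 24 hours before each study visit". Section 6.2 sets the rule during the study: "subjects must refrain from the use of salivary stimulants within 24 hours prior to each study visit". Section 18 ties the same period to saliva collection: "Salivary stimulants may not be used in this protocol within 24 hours prior to saliva collection". Section 7.10 acknowledges the consequence: "this suspension could cause discomfort from dryness of the mouth".

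Section 9.2 lists as a secondary endpoint "Changes in assessments on the Patient Dry Mouth Questionnaire from Day 0 to study Days 14, 28, 42, and 56", with a parallel endpoint for the index. Section 10.1.6 summarises both by visit and, for symptom items, by shift tables against Day 0. McNemar's test follows where a shift looks substantial, GEE is possible, and any resulting p-values are labelled exploratory.

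**The concern.** The protocol standardises stimulant status for salivary flow but not for the baseline of the symptom endpoint. A subject who takes pilocarpine or cevimeline and fills in the Day 0 questionnaire two days early may do so while on the drug. On Days 14, 42 and 56 she answers after at least 24 hours without it. By the protocol's own account that interval can make the mouth drier, so her change from Day 0 can mix the effect of irrigation with the effect of stopping a stimulant.

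The likely direction is apparent worsening, which could hide a real improvement in symptoms or look like harm. The questionnaire is the patient-reported symptom endpoint in Section 9.2, so it is where a reader would look for whether any gain in flow is felt.

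The saline-irrigated gland, which protects the flow comparison, gives no protection here. The questionnaire is answered once per subject, and every subject has one gland treated with each solution. The symptom comparison is before against after, with no control.

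**Working it through.** The protocol states no figure on this point, so there is nothing to reproduce. The check is a comparison of time windows, followed by an illustration of size.

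**Step 1: windows.** The early option lies 2 days, about 48 hours, before the visit (Table 4-1, footnote 3). The hold covers 24 hours before the visit (Sections 3.3, 6.2 and 7.10) or before saliva collection (Sections 11.5 and 18). Since 48 > 24, an early assessment falls before the hold begins.

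| Assessment | Permitted timing | Stimulant hold |
|---|---|---|
| Day 0, Day 28: early option | 2 days before the visit | outside |
| Day 0, Day 28: alternative | at the visit, before saliva collection | inside |
| Days 14, 42, 56 | at the visit | inside |

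**Step 2: does the early session have its own hold?** Nothing says so. Footnote 3 defines it relative to the visit. The minimum of 7 clinic visits in Section 4.1 is already filled by Stage I, Stage II and Days 0, 14, 28, 42 and 56 (2 + 5 = 7). No saliva is collected at the early session.

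**Step 3: direction.**
- *Days 14, 42 and 56.* If Day 0 was early (on stimulant) and follow-up is at the visit (off stimulant), the artefact is toward more dryness.
- *Day 28.* If Days 0 and 28 use the option in the same way, the artefact cancels between them. If only Day 0 was early, it is toward worsening. If only Day 28 was early, it is toward improvement.

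**Step 4: size, as illustration only.** Let *u* be the share of subjects on stimulants, *o* the share of those assessed early at Day 0, and *w* the chance that a dryness item worsens off the stimulant. The protocol gives none of these. Expected artefactual shifts among the 16 treated subjects are 16 × *u* × *o* × *w*:
- low end: 16 × 0.25 × 0.25 × 0.3 = 0.3
- middle: 16 × 0.5 × 0.5 × 0.6 = 2.4
- high end: 16 × 0.75 × 1.0 × 0.6 = 7.2

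For a binary item with *k* shifts all in one direction, the exact two-sided McNemar p-value is 2 × 0.5^*k*:
- *k* = 5: 0.0625
- *k* = 6: 0.031

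The binomial probability of at least 6 such shifts in 16 is about 0 at the low end, 0.02 in the middle case and 0.80 at the high end.

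**The case against.** Much of the case against stands and limits the point.

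- **The option is permissive.** Day 0 may equally be assessed at the visit, inside the hold. The effect needs a stimulant user, an early assessment and an item that responds to a day off the drug. A reader might infer that change from Day 0 always contains a withdrawal effect; the protocol supports only that it can.
- **Stimulant use may be uncommon.** Section 1.1 describes stimulants as helping few patients and being poorly tolerated by many, which favours the lower part of the range. Six one-way shifts would need 37.5% of the 16 subjects (6/16).
- **The instruments are not shown.** Recall periods are unknown, and a long one would dilute the effect. Section 10.1.6 mentions tooth decay rate among the items, which a one-day hold would hardly move.
- **The index is a different kind of measure.** "The clinician will use the Sjögren's Disease Activity Index to assess disease activity in each subject", and nothing shown indicates that any of its items responds to a 24-hour hold. It is tempting to extend the point to the index because footnote 3 covers both, but that extension is unsupported.
- **The analysis is descriptive.** Any McNemar or GEE p-values are exploratory.

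Two further arguments carry less weight. Both instruments are also completed at Stage II, which might supply a pre-treatment value taken under the hold, but Section 9.2 defines the endpoint against Day 0. Concomitant medications are reviewed at each visit, so users may be identifiable and an analysis plan could flag them. However, Table 4-1 does not ask for stimulant status at the early session, and no analysis plan can restore what was not recorded then.

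**Conclusion.** The point holds in a limited form. Footnote 3 and the hold rules together allow the Day 0 questionnaire to be answered under a different stimulant status from Days 14, 42 and 56. For stimulant users who take the early option, change from Day 0 on current-dryness items can then include a withdrawal effect, most likely apparent worsening, with no placebo contrast to cancel it.

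The size cannot be fixed from the protocol. It runs from negligible (0.3 expected shifts of 16) to material (7.2 of 16), depending on the number of users, uptake of the option and how far the items reflect current dryness. All of these are assumptions.

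A reader might infer that the primary result is at risk. It is not: salivary flow is collected at the visit, inside the hold, on Day 0 and on every later study day. The affected endpoint is secondary and mainly descriptive. Severity is low to moderate, and the case for acting rests largely on how cheap the correction is.

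**What to change.** Remove the two-days-before option from footnote 3 of Table 4-1, leaving the alternative it already contains: completion at the visit, before saliva collection, on Days 0 and 28. The questionnaire would then be answered under the same hold at Day 0 and at every later visit. Apply the change to the index as well for consistency, although no effect on it is shown. The hold itself is not altered.

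Where assessments have already been taken early, record whether the subject was within the hold at that moment, and compare only assessments made under the same status.

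The cost is one footnote in an amendment and, for subjects who would have used the early option, up to about 45 minutes more at each of the Day 0 and Day 28 visits: 15 minutes for the questionnaire (Section 4.4.4) plus 30 for the index (Section 4.4.5). The symptom scores remain uncontrolled before-and-after data; the change removes one avoidable source of bias from them.

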#### 4.4.1 Vital Signs Measurement

Vital signs measurements will include pulse rate, systolic and diastolic blood pressure, respiratory rate, and temperature. Vital signs will be done at Screening Stage I and Stage II, Day 0, 14, 28, 42, 56 and follow-up (if done in clinic). Vital sign measurements take about 10 minutes to complete.

#### 4.4.2 Medical history and examination

A medical and medication history will be reviewed at Screening Stage I and an oral and physical exam will be done at Screening Stage I, Day 0, 28, 56 and Safety follow-up (if clinically indicated) to assess overall physical health. The exam will be targeted toward the assessment of Sjögren's and not include a full gynecological exam. These procedures take up to an hour to complete.

#### 4.4.3 Collection of Saliva/Measurement of Salivary Flow Rate

Saliva will be collected separately from both parotid glands at the following time points: Screening Stage I and Days 0, 14, 28, 42, and 56. The collection will take place before any saline or treatment irrigation (Screening and Days 0 and 28). The saliva collection procedure is noninvasive and requires no anesthesia. A Teflon collection cup will be placed over the parotid duct orifice and held in place by slight negative pressure. Parotid saliva, either at rest or following a physiologic gustatory stimulus with 2% citric acid, will be allowed to flow freely via plastic tubing connected to the collection cup. The Salivary Flow Collection Procedure is provided in Appendix 24.6. This procedures takes up to 30 minutes to complete.

Saliva samples will be used for the following: 1) identification of changes in proteins involved in calcium signaling, such as Stim1. In vitro and in vivo studies with salivary gland cell lines and primary cells will be run in parallel to examine the effect of dexamethasone on the epithelial cells, 2) exosomal microRNA biomarkers of inflammation. Saliva collected during the study will be used for isolation of exosomes, and the nucleic acid content of the exosomes will be correlated with the inflammatory status of the glands. Real-time quantitative polymerase chain reaction assays, microRNA microarrays, and/or deep sequencing will be used for identifying microRNAs.

